X-ray and surgeon appointment	Х						
Surgery report (only surgical group)		Х	X^*	X^*			
CT	Х						
Patient reported outcomes							
WOOS ^a	Х		Х	Х	Х	Х	Х
DASH ^b	Х		Х	Х	Х	Х	Х
EQ-5D-5L°	Х		Х	Х	Х	Х	Х
iPCQ ^d			Х	Х			
VAS ^e	Х		Х	Х	Х	Х	Х
Physical activity							
Tri-axial accelerometry	Х			Х			
Treatment related variables							
Adverse events ^f			Х	Х	Х	Х	Х
Serious adverse events ^f			Х	Х			
Training-compliance			Х				
Pain before exercise and at the end of			v				
exercise for the exercise group using NRS ^g			Х				
Other shoulder related treatments	Х		Х	Х			
Analgesic consumption in last week	Х		Х	Х	Х	Х	Х
Crossover			Х	Х	Х	Х	Х

Table 1. Assessments and procedures.

m = months. y = years. *X-ray at 3 months for the surgical group only to assess adverse events. ^a the Western Ontario Osteoarthritis of the Shoulder index (WOOS). ^b Disabilities of the Arm, Shoulder and Hand (DASH). ^c European Quality of life 5 Dimensions with 5 Levels (EC-5D-5L). ^d Productivity Costs Questionnaire (iPQC) only in Denmark. ^c Visual Analogue Scale will be at rest, during activity and at night. ^f Described in "Adverse events". ^g Numeric Rating Scale will be used at the supervised exercise sessions to determine pain at rest before and after the session.

	TSA group	Exercise group
	n =	• •
Gender, n (%) female		
Age, mean (SD) years		
Body mass index, mean (SD) kg/m ²		
Handedness, n (%) right		
Affected shoulder, n (%) right		
Duration of shoulder symptoms, n (%)		
6-12 months		
1-2 years		
2-5 years		
More than 5 years		
Previous treatment in the affected shoulder, n (%) yes		
Exercise and/or physiotherapy		
Pharmacological treatment		
Surgical treatment		
Civil status, n (%)		
Living alone		
Living with someone		
Not informed		
Educational level, n (%)		
Low		
Medium		
High		
Employment status, n (%)		
Employed		
Outside the labor market		
In activation, sick leave, available, etc.		
Retired		
Alcohol consumption, n (%)		
Under 2 items per week		
2-7 items per week		
8-14 items per week		
15-21 items per week		
Over 21 items per week		
Smoking behaviour, n (%)		
Never smoked		
Quit smoking		
Sometimes		
Daily		
Co-morbidities, n (%) yes		

Table 2: Baseline characteristics for the two intervention groups

Table 3: Intention to treat analysis and per protocol analysis of the between group
difference for the surgical group and exercise group in end-scores one year after
intervention.

		-	Intention	-to-treat an	alysis		
		TSA			Exercise		Improvement between the two groups
	Baseline	Three months	One year	Baseline	Three months	One year	Adjusted
WOOS							
DASH							
Pain at rest							
Pain during							
activity							
Pain at night							
Use of							
analgesics*							
Adverse events*							
			Per-pr	otocol analy	ysis		
		TSA			Exercise		Improvement
							between the two
							groups
	Baseline	Three	One	Baseline	Three	One	Adjusted
		months	year		months	year	
WOOS							
DASH							
Pain at rest							
Pain during							
activity							
Pain at night							
Use of							
analgesics*							
Adverse events*							

Higher scores indicate desired (better) treatment outcome for WOOS. For the other outcomes lower scores indicate desired (better) treatment outcome.

*Analysed with risk difference, use of analgesics (yes/no), adverse events (yes/no).

	TS	Α		Ex	ercise		Cr	055-0V	er	No treatment		ıt	Improvements between the four groups	
	В	3M	1Y	В	3M	1Y	B	3M	1Y	В	3M	1Y	Adjusted	
WOOS														
DASH														
Pain at rest														
Pain during activity														
Pain at night														
Use of analgesics*														
Adverse events*														

Table 4: As treated analysis of the between group difference for the surgical group and exercise group in end-scores one year after intervention.

B=Baseline, 3M=Three months, 1Y=One year

Table 5: Usage of painkillers

		TSA group			Exercise gro	up
	Baseline	Three months	One year	Baseline	Three	One year
					months	
Use of painkillers, n (%) yes						
Type of painkillers, n (%)						
Paracetamol						
NSAID						
Morfin/opiods						
Other painkillers						
Usage of painkillers, n (%)						
Never						
Monthly						
Weekly						
Daily						

Table 6: Adverse and serious adverse events

	TSA group	Exercise group
Adverse events, n (%)		
Postoperative infections		
Instability		
Periprosthetic fracture		
Loosening		
Humeral component		
Glenoid component		
Both		
Injuries related to the exercise intervention		
Serious adverse events, n (%)		
Death		
Embolism		
Liver failure		
Renal failure		

*Serious adverse events resulting in the need for hospitalization or death in the first 4 weeks after surgery. Adverse events that occurred between baseline and 12 months follow-up but did not necessarily have a causal relationship between the treatments.

Table 7: Adherence to randomized treatment

	Exercise group
Training adherence	
Showed up for supervised sessions within the first three months of exercise, mean	
(SD)	
Participated in at least 70% of supervised sessions within the first three months of	
exercise, n (%)	
Number of self-reported exercise sessions within the first three months of exercise,	
mean (SD)	
Completed three or more exercise sessions per week within the first three months of	
exercise, n (%)	
Completed 4 booster sessions, n (%)	
Number of self-reported exercise sessions from three months to one year, mean (SD)	
Completed three or more exercise sessions per week from three months to one year, n	
(%)	
Number of patients randomized to exercise undergoing surgery in the follow-up	
period, n (%)	
	Surgical group
Surgical adherence	
Number of patients randomized to surgery electing not to undergo surgery in the	
follow-up period, n (%)

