In hip and knee OA exercise is recommended as the first-line treatment (4). The effectiveness of exercise and the effectiveness of TSA in patients with glenohumeral OA is unknown, as no randomized trials have directly compared TSA to a non-surgical treatment (5). In order to provide a trustworthy and evidence-based foundation for clinical decisions it is important to conduct a randomized controlled trial where surgical treatment is compared to non-surgical treatment in patients with glenohumeral OA.

The primary aim of this trial is to examine if surgical treatment followed by standard care is superior to a 12-week exercise programme in patients with primary glenohumeral OA. The primary outcome is the Western Ontario Osteoarthritis of the Shoulder index score (WOOS), measured 12 months after initiating the treatment. The primary hypothesis is that surgical intervention is superior to the exercise intervention at 12 months (1).

The key secondary objectives are (1):

- To investigate the effectiveness of total anatomical shoulder arthroplasty followed by standard rehabilitation compared to a 12-week physiotherapist-supervised exercise programme, on (1) pain intensity, (2) activities of daily living, (3) use of analgesics and (4) shoulder-related quality of life in patients with glenohumeral OA.
- 2. To investigate the safety of total anatomical shoulder arthroplasty followed by standard rehabilitation compared to a 12-week physiotherapist-supervised exercise programme on occurrence of adverse events from baseline to 12 months after initiating the treatment, in patients with glenohumeral OA.

Exploratory objectives:

- 1. To investigate the external validity of the randomised controlled trial on total anatomical shoulder arthroplasty and physiotherapist-supervised exercise in patients glenohumeral OA by comparing patient characteristics and patient-reported WOOS scores from baseline to 12 months after initiating the treatment, in patients included in the randomised controlled trial versus those declining to participate but included in the follow-up cohort.
- 2. To investigate objectively measured physical upper extremity activity level from baseline to 12 months using tri-axial (Axivity, UK) accelerometers, in patients with glenohumeral OA eligible for total anatomical shoulder arthroplasty.

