The sample size is based on the expected between group difference in the WOOS end scores. The WOOS score 1 year after TSA surgery was 84.6 points in the Danish Shoulder Arthroplasty Registry in 2020 (7). The WOOS score after completing this exercise intervention in a feasibility study was 67 points (15). The assumed common SD was 27.1. The required power was set to 80%. Given a power of 0.80 to detect a difference between the two groups and using a two-sided significance level α =0.05, the estimated sample of each intervention group is 39 patients. Allowing for possible crossovers, loss-to follow-up and drop-outs the total number of patients in each group is 51 (1).

Framework

The overall objective of the trial is to determine whether surgical intervention results in a clinically and statistically significant greater improvement compared to exercise on WOOS, Disabilities of the Arm, Shoulder and Hand (DASH) (16), patient-reported pain intensity at rest, during activity, and nightly pain using the 100 mm VAS, the use of analgesics during the last week (paracetamol, NSAID, opioids) and adverse events. The primary hypothesis is that surgical intervention is superior to the exercise intervention at 12 months.

Blinded interpretation of the results

The blinded interpretation will be of the intention-to-treat analysis. The blinded analysis involves the primary outcome and key secondary outcomes. The principal investigator (JBL) will export data from REDCap and deliver the blinded dataset for analysis to the statistical analysist (AR). The senior statistician (EP) will supervise the analysis. The blinded results from the analysis of treatment A compared with treatment B will be presented to the project group followed by the development of the blinded interpretation. Interpretation version 1 assumes that group A had surgery, while interpretation 2 assumes that group A performed exercise. A draft of the blinded interpretation will be sent for approval by all co-authors. No other outcomes will be analyzed prior to an agreement of the blinded interpretation by all co-authors. All other analyses described in this document will be performed after the blinded interpretation is published (17).

Statistical interim analysis and stopping guidance

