- 7. Other reasons for exclusion include mentally unable to participate or planned absence for more than 14 days in the first 3 months after baseline test
- 8. Unable to communicate in the respective languages of the participating countries.

Recruitment

The CONSORT flowchart will present the number of patients screened, excluded (with reasons), eligible for inclusion, randomized, receiving allocated treatment, withdrawals (with reasons), lost to follow-up (with reasons), included in the ITT analysis, included in the per protocol analysis.

Withdrawal/follow-up

Throughout the trial period the patients are allowed to withdraw from the study at any time. Patients who decide to withdraw will be encouraged to continue in the study as if they have received the intervention. Withdrawal will be classified into two options; (1) complete withdrawal from the study with no further follow-up and data-collection, (2) consent to follow-up assessments and data-collection. The number of withdrawals and the timing of withdrawal will be presented in the CONSORT flowchart (with reasons).

Baseline patient characteristics

Baseline characteristics will be presented as seen in Table 2. Categorical variables will be presented as numbers and percentages. Continuous variables will be presented as mean with

standard deviation (SD), if normally distributed and ad median with interquartile range (IQR) if not normally distributed. No tests of significance will be conducted for the baseline characteristics, imbalances of importance will be noted. Baseline and follow-up values for the primary and secondary outcomes will be presented as part of the analysis, as seen in Table 3.

SECTION 6: ANALYSIS

Outcome definitions

The Western Ontario Osteoarthritis of the Shoulder index score (WOOS)

The primary outcome will be presented as the between group difference on the 12-month follow-up score. WOOS is a valid and reliable patient-reported questionnaire assessing shoulder pain and function in a total raw score ranging from 0-1900, raw scores can be converted to a score from 0-100, where 0 indicates severe problems and 100 indicates no problems.

Key secondary outcomes

Disabilities of the Arm, Shoulder and Hand (DASH) (Lindenhovius et al. 2008); patientreported pain intensity at rest, during activity, and nightly pain using the 100 mm VAS; the use of analgesics during the last week (paracetamol, NSAID, opioids); serious adverse events and adverse events.

Analysis methods

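### The Table 6 footnote ties serious adverse events to a 4-week post-surgical window, so the two arms are not counted by a comparable rule

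*SAP*

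**What the plan says.** The footnote to Table 6 holds two sentences with different windows. Serious events are described as "Serious adverse events resulting in the need for hospitalization or death in the first 4 weeks after surgery". Other events are described as "Adverse events that occurred between baseline and 12 months follow-up but did not necessarily have a causal relationship between the treatments". Only the first window depends on an operation.

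The related places in the SAP are:

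- **Table 6, body.** The serious-event block lists death, embolism, liver failure and renal failure, with a TSA and an exercise column.
- **Table 1.** The row "Serious adverse events ^f" is marked at 3 and 12 months and is not labelled as surgical-only, although the surgery report row is. Its note f points to a description of adverse events that is not in the SAP.
- **Section 6, Key secondary outcomes.** The list ends with "serious adverse events and adverse events".
- **Key secondary objective 2 (safety).** The arms are compared "on occurrence of adverse events from baseline to 12 months after initiating the treatment".
- **Blinded interpretation of the results.** "The blinded analysis involves the primary outcome and key secondary outcomes".
- **Section 6, Harms.** Counts and percentages are planned for each event. No window is given.

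**The concern.** A window that opens at surgery has no starting point in a patient who has no surgery. Applied to the whole serious-event block, the rule excludes every exercise patient who does not cross over, and every patient randomised to TSA who is not operated. The SAP foresees both groups under Adherence and protocol deviations. A serious event after week 4 in an operated patient would also not be shown as serious.

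Table 6 would then set side by side two counts that do not measure the same thing. A zero in the exercise column could be taken as observed safety when it follows largely from the rule. The blinded interpretation would work from the same counts.

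**Working it through.** **Step 1: the possible readings of the footnote.**

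| Reading | Operated patient | Never-operated patient |
|---|---|---|
| The 4-week limit covers hospitalization and death | Counted for 4 weeks only | Never counted |
| The limit covers death only | Deaths counted for 4 weeks; hospitalization has no stated window | Deaths never counted; hospitalization has no stated window |
| The footnote is meant for the surgical arm only | Counted for 4 weeks | No rule stated |

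No reading gives both arms the same rule for all serious events. Nothing else in the SAP supplies one: Harms states no window, and Tables 3 and 4 have only an adverse-event row, so Table 6 is the only table that shows serious events.

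**Step 2: countable patient-time on the first reading.** The SAP states no figure to reproduce here. The inputs are 39 and 51 patients per group (Sample Size), a 4-week window (Table 6 footnote) and 52 weeks of follow-up. I assume one full 4-week window per operated patient and no censoring.

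- Patient-weeks per arm: 51 × 52 = 2,652.
- Allowance for crossover, loss and drop-out together: 51 − 39 = 12, or 12/51 = 23.5%.
- TSA arm, all operated: 51 × 4 = 204; 204/2,652 = 7.7%.
- TSA arm, 12 not operated: 39 × 4 = 156; 156/2,652 = 5.9%.
- Exercise arm, no crossover: 0/2,652 = 0%.
- Exercise arm, 12 crossovers: 12 × 4 = 48; 48/2,652 = 1.8%. Even then 39/51 = 76.5% of the arm has no countable serious event.

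The SAP does not split the allowance, so giving all 12 to crossover, or all 12 to TSA patients without surgery, is a bounding case within that allowance. On the death-only reading these shares apply to deaths alone.

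**Step 3: what this could mean in events.** The 12-month risk p is my assumption, because the SAP gives none. Take the same constant hazard in both arms, 51 patients per arm, all TSA patients operated and no crossover. The risk inside the window is r = 1 − (1 − p)^(28/365).

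| Assumed p | Events per arm over 12 months (51p) | Counted in TSA (51r) | Counted in exercise | Apparent TSA minus exercise difference (true value 0) |
|---|---|---|---|---|
| 2% | 1.0 | 0.08 | 0 | 0.15 percentage points |
| 5% | 2.6 | 0.20 | 0 | 0.39 percentage points |
| 10% | 5.1 | 0.41 | 0 | 0.80 percentage points |

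The spurious difference is small. The larger effect is that most events are not shown as serious in either arm. If serious events cluster soon after surgery, more of the TSA events would be kept than the constant hazard implies.

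**The case against.** A reader might infer that the footnote flatly contradicts Table 6 and Table 1. The SAP does not support that.

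- Every row of Table 6 has both columns, including rows such as loosening and periprosthetic fracture. A column therefore does not promise that the event can occur in every patient of that arm.
- Exercise patients who cross over to TSA stay in the exercise arm under intention to treat, so their post-surgical events can fill that column.
- Visits at 3 and 12 months can record an earlier event, including one after delayed or crossover surgery.
- The safety objective names only adverse events, and the key secondary list gives no window.

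These are mismatches, not strict contradictions.

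A reader might also infer that the exercise count must be zero. That fails for crossovers, and on the death-only reading it fails for hospitalization due to embolism, liver failure or renal failure. Nor does the SAP show which arm gains overall: serious events in the TSA arm after week 4 are left out too.

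Three further limits stand. The description cited in Table 1 note f may lie in the protocol and may settle the definition. The footnote's asterisk has no visible anchor in the text at hand, although its wording names serious events. Late serious events may still enter the adverse-event (yes/no) count, which runs to 12 months.

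What does not stand is the argument that this is only a definition left to the protocol. The footnote states a counting rule, the only one for serious events in the SAP, and following it would mislead.

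**Conclusion.** The point holds in this form: under the footnote as written, serious events are not counted comparably in the two arms. On the fuller reading, countable time is 5.9% to 7.7% of the year in the TSA arm and 0% to 1.8% in the exercise arm, given the SAP's group sizes, its pooled allowance of 12 and no censoring. On the death-only reading the problem is confined to deaths, and hospitalization lacks a window.

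These are shares of patient-time, not of events. The number of events affected is unknown, and so is the net direction of error. Confidence is moderate, because the wording is ambiguous and the cited description is not at hand. The point matters because a key secondary outcome is affected and an exercise-arm zero could be misread; it should be settled before the blinded results are produced.

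**What to change.** Reconcile the Table 6 footnote with the safety objective, the key secondary outcomes, Table 1 and the description cited in its note f. Serious events should be counted in both arms over one common window that is not conditional on surgery; the SAP's own period from baseline to 12 months serves. If the cited description already contains such a definition, cite it and align the footnote. The 4-week post-surgical count can be kept, if wanted, as a descriptive sub-row.

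The cost is one reworded footnote and at most one extra row. Table 1 already schedules serious events at 3 and 12 months, so no new visit is needed. The small downside is that some events already recorded may have to be reclassified.

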Descriptive statistics will be presented as means with standard deviation (SD) for all normally distributed continuous variables. Continuous variables that do not follow a normal distribution will be presented as median with interquartile ranges. Normal distribution will be determined by visual inspection of QQ-plots and histograms. Categorical outcomes will be presented as numbers with percentages.

The primary comparison in WOOS between groups will be conducted using a linear mixed model. Intervention group and time (3 months, 12 months) will be included as fixed effects and patient as random. Baseline score, sex, age and study site will also be included as fixed covariates. Interaction between study group and time will be included in the model to estimate treatment effect at each time point. 95% confidence intervals are estimated for each time point.

Due to the repeated mixed model analysis no missing data imputation will be conducted. A sensitivity analysis will be done using an analysis of covariance (ANCOVA) including baseline score, sex, age and study site as covariates with the same ITT approach for time (3 months and 12 months) separately.

Analysis for patient-reported DASH, pain intensity at 3 and 12 months will be analysed similar to the primary comparison. For binary variables (ie. the use of analgesics and adverse events) we use proportions to describe the number of events. For each binary outcome an unadjusted risk difference in proportions with 95% confidence interval of outcomes between study groups. Table 3 illustrates the primary analysis.

Response to treatment for the WOOS change score from baseline to 12 months and 3 months follow-up will be computed for each patient in both treatment groups. Response to treatment will be presented dichotomized (i.e. responder and non-responder) as number and percentage. The patients will be classified as a responder if they reach a minimal important change of 13.3 points or more from baseline to 12 months follow-up (19).

Missing data

As stated above, imputations will not be applied in this study due to the repeated mixed model analysis. Each randomized patient will be included in the intention-to-treat analysis with the collected data. In an attempt to collect data from all randomized patients, patients deciding to withdraw from the study, are still encouraged to attend the follow-up test.

Harms

Adverse and serious adverse events will be presented as number and percentage for each event.

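### Table 6 is inconsistent on what counts as a serious adverse event: the footnote goes by consequence, the rows go by event name

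*SAP*

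**What the plan says.** The Key secondary outcomes paragraph of SAP Section 6 closes its list with "serious adverse events and adverse events". The Harms paragraph gives the reporting rule: "Adverse and serious adverse events will be presented as number and percentage for each event". It does not say how an event is sorted into one class or the other.

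Table 6 has two blocks.

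- The adverse-event block lists "Postoperative infections", instability, "Periprosthetic fracture", loosening (humeral component, glenoid component or both) and injuries from the exercise programme.
- The block headed "Serious adverse events, n" (%) lists death, embolism, liver failure and "Renal failure", and nothing else.

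The footnote to the table describes the serious class as "Serious adverse events resulting in the need for hospitalization or death in the first 4 weeks after surgery". It describes the other class as "Adverse events that occurred between baseline and 12 months follow-up but did not necessarily have a causal relationship between the treatments".

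**The concern.** Hospitalisation or death is a consequence, and any type of event can have it. A list of four names is a different kind of rule. The table uses both and does not say which governs. The complications most specific to the operation have a row only in the adverse-event block, and no row is split by seriousness. Whoever fills the shell must therefore choose between following the rows and following the footnote, and the two choices can give different serious-event counts from the same data.

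Safety is a stated objective of the trial. The section on blinded interpretation also includes the key secondary outcomes in the results that are interpreted with arms masked. If the classification is still open at that stage, it will be settled by whoever compiles the table rather than by the plan.

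**Working it through.** The SAP states no figure for this outcome, so there is nothing to reproduce. The check sets rows against footnote, followed by a short scale calculation.

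**Step 1: run example records through both parts of Table 6.**

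| Record | By the footnote | By the rows |
|---|---|---|
| Infection in week 2 after surgery, readmitted | Serious | Adverse-event row only |
| Periprosthetic fracture in week 3 after surgery, readmitted | Serious | Adverse-event row only |
| Embolism in week 1 after surgery, admitted | Serious | Serious row |
| Embolism in month 6 in an exercise patient never operated on, admitted | No surgery date, so the window cannot apply | Serious row |

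Rows and footnote agree only on the third record. The first two are the undercount risk among operated patients. The fourth shows that the disagreement is not confined to surgery: the footnote has no meaning for a patient without an operation, although the row exists for both arms.

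**Step 2: compare the windows.** The footnote's serious window is 4 weeks, and 28/365 = 7.7% of a year. The safety objective in the SAP runs from baseline to 12 months in both arms, and Table 1 schedules serious adverse events at 3 and 12 months. The window therefore needs reconciling together with the criterion.

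**Step 3: size per patient.** The planned number per arm is 51 (Sample Size section). One patient without a serious row is 1/51 = 1.96 percentage points of the arm; three are 3/51 = 5.88 points.

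**Step 4: how many patients (illustration only).** The SAP gives no rate. Let p be the assumed share of 51 TSA patients who are hospitalised within the window for an event listed only in the adverse-event block. The expected number is 51 × p, and the chance of at least one is 1 − (1 − p)^51.

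| Assumed p | Expected patients | Chance of at least one |
|---|---|---|
| 0% | 0 | 0% |
| 1% | 0.5 | 40% |
| 2% | 1.0 | 64% |
| 4% | 2.0 | 88% |
| 6% | 3.1 | 96% |

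This shows scale, not an estimate. At p = 0% nothing is lost.

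**The case against.** Several counter-arguments have force.

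- **No sentence calls a hospitalised infection or fracture non-serious.** If the footnote governs, such an event is serious and nothing is misfiled. This stands: misclassification is a risk of filling the shell literally, not a stated rule.
- **The footnote may only restrict the four listed events** rather than define the class. It is a sentence fragment, and in the text available its asterisk is attached to no visible row. This reading is possible, but the SAP does not choose it, and it leaves the status of a readmitted infection open.
- **The definition may be in the protocol.** Table 1 refers both classes to a description under adverse events that the SAP does not contain. That may settle the criterion, but it would not supply the rows missing from Table 6.
- **The heading of the serious block may itself be a total row.** It may. The SAP does not say so, nor whether such a total would include events that have a row only in the other block.
- **No between-arm contrast of serious events is explicitly planned.** The note to Table 3 applies the risk difference to analgesic use and adverse events, each yes/no, and the table has no row for serious events. This stands: the effect falls mainly on the descriptive Table 6, where infections and fractures are still shown by arm.

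A reader might go further and infer that the plan makes surgery look safer than exercise. The documents do not support that. The missing rows can lower the serious count among operated patients, but the surgery-based window means that never-operated exercise patients cannot meet the footnote at all, which pushes the comparison the other way.

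**Conclusion.** The contradiction between rows and footnote is real and can be seen within Table 6 alone. Read literally, the shell gives no serious row to an operated patient who meets the footnote through infection, instability, periprosthetic fracture or loosening. A key secondary outcome can therefore be undercounted among operated patients by 1.96 percentage points of an arm per patient affected. That figure assumes 51 patients in the denominator.

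The number affected cannot be derived from the SAP, and neither can the share of all serious events that would be missed. The net direction of any bias between arms is not established. The point warrants a change to the plan because two parts of one table disagree, not because a detail has been left to the protocol.

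**What to change.** Before blinded results are seen:

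1. Reconcile rows and footnote into one seriousness criterion and one time window, confirmed by the trial team and applicable to both arms, including patients who are never operated on.
2. Classify every recorded event by that criterion, whatever its name.
3. In Table 6, show serious and non-serious counts for each event type.
4. Add an explicit row by arm for patients with any serious adverse event, n (%). Attach a risk difference with 95% CI only once the criterion applies to both arms. On the present footnote, such a contrast would compare operated patients with patients who cannot meet the definition.

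The cost is a few sentences of SAP text and a revised table shell. The footnote already requires hospitalisation status for events after surgery; if the agreed criterion uses it over a wider window, the team should confirm that it is recorded for both arms. The downsides are a longer table and possibly a higher serious-event count after surgery.
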